PROTOCOL

| TITLE | High Frequency Oscillatory Ventilation Combined with |
|------------------|--|
| | Intermittent Sigh Breaths in Neonate: Effect on Carbon Dioxide |
| | Level |
| NCT number | NCT05682937 |
| Principal | [name] |
| Investigator | |
| Co-investigator | [name] |
| | [name] |
| | [name] |
| | [name] |
| | [name] |
| All investigator | Division of Neonatology, Department of Pediatrics, Faculty of |
| | Medicine, Prince of Songkla University, Songkhla, Thailand |
| Keywords | Carbon Dioxide, High-Frequency Ventilation, Sigh Breath, |
| | Newborn |

Background and rationale

Pulmonary disease continues to be the major cause of morbidity and mortality in very preterm infants.⁽¹⁾ Neonatal intensive care units (NICU) across the world have successfully used conventional ventilation (CV), high-frequency oscillatory ventilation (HFOV), and high-frequency jet ventilation (which is currently not available in Thailand) to manage respiratory failure in newborn.⁽²⁾ Non-synchronized CV, the earliest mode of ventilation used in neonates, was designed to emulate tidal respirations typical of newborns.⁽³⁾ Synchronized ventilation improves gas exchange; increases patient comfort with decreased need for sedation and muscle relaxation; reduces airway pressures; decreases work of breathing, risk of barotrauma and volutrauma; and provides faster weaning from mechanical ventilation.⁽⁴⁾

In order to avoid distortion of the lung caused by the large swings in pulmonary pressures during CV at rates of 30 to 80 breaths per minute, HFOV at rates of 600 to 800 breaths per minute with very small tidal volume (TV) was developed (**Figure 1**). HFOV allows for low TV, and minimizing volutrauma and shear force injury by using of TVs that are smaller than physiologic dead space (<3 mL/kg) that oscillate around a set mean airway pressure (MAP) at rates ranging from 300 to 900 breaths per minute (5–15 Hz).⁽⁴⁾ Gas exchange occurs from multiple processes, including Taylor dispersion, molecular diffusion, regional variation in turbulent and laminar flow, and pendelluft movement of air. Exhalation on HFOV is active, in contrast to the passive exhalation seen with high-frequency jet ventilation, and adjustments in amplitude, frequency, and MAP can modulate infant oxygenation and ventilation.⁽⁴⁾

[figure not shown]

Fig. 1 Schematic representation of the purported waveforms of HFOV and conventional pressure-controlled ventilation in the distal airways. The large pressure swings present in the proximal circuit during HFOV (perhaps up to twice the mean airway pressure, depending on the set ΔP) are significantly attenuated in the distal airways. The degree of attenuation is dependent on frequency, ETT size, and inspiratory/expiratory time ratio.

| Comparison 1. | HFOV versus | s CV | (all trials) |
|---------------|-------------|------|--------------|
|---------------|-------------|------|--------------|

[figure not shown]
| Outcome or subgroup title | No. of studies | No. of partici- pants | Statistical method | Effect size |
|---|-------------------|-----------------------------|---------------------------------|-------------------|
| 1 Death by 28 to 30 days | 10 | 2148 | Risk Ratio (M-H, Fixed, 95% CI) | 1.09 [0.88, 1.34] |
| 2 Mechanical ventilation at 28 to 30 days in survivors | 3 | 767 | Risk Ratio (M-H, Fixed, 95% CI) | 1.08 [0.86, 1.35] |
| 3 Oxygen at 28 to 30 days in survivors | 6 | 1043 | Risk Ratio (M-H, Fixed, 95% CI) | 0.98 [0.88, 1.10] |
| 4 CLD at 28 to 30 days (O ₂ + x-ray) in sur- vivors | 4 | 820 | Risk Ratio (M-H, Fixed, 95% CI) | 0.86 [0.74, 1.01] |
| 5 Death or CLD at 28 to 30 days | 5 | 1160 | Risk Ratio (M-H, Fixed, 95% CI) | 0.94 [0.85, 1.04] |
| 6 Death by 36 to 37 weeks or discharge | 17 | 3329 | Risk Ratio (M-H, Fixed, 95% CI) | 0.95 [0.81, 1.10] |
| 7 CLD at 36 to 37 weeks PMA or discharge in survivors | 17 | 2786 | Risk Ratio (M-H, Fixed, 95% CI) | 0.86 [0.78, 0.96] |
| 8 Death or CLD at 36 to 37 weeks PMA or discharge | 17 | 3329 | Risk Ratio (M-H, Fixed, 95% CI) | 0.90 [0.84, 0.97] |
| 9 Any pulmonary air leak | 13 | 2854 | Risk Ratio (M-H, Fixed, 95% CI) | 1.19 [1.05, 1.34] |
| 10 Gross pulmonary air leak | 11 | 2185 | Risk Ratio (M-H, Fixed, 95% CI) | 1.13 [0.88, 1.45] |
| 11 Intraventricular haemorrhage - all grades | 12 | 3084 | Risk Ratio (M-H, Fixed, 95% CI) | 1.04 [0.95, 1.14] |
| 12 Intraventricular haemorrhage - grades 3 or 4 | 18 | 4069 | Risk Ratio (M-H, Fixed, 95% CI) | 1.10 [0.95, 1.27] |
| 13 Periventricular leukomalacia | 17 | 3983 | Risk Ratio (M-H, Fixed, 95% CI) | 1.03 [0.81, 1.31] |
| 14 Retinopathy of prematurity (stage 2 or greater) in survivors | 12 | 2781 | Risk Ratio (M-H, Fixed, 95% CI) | 0.81 [0.70, 0.93] |

Fig. 2 Results from meta-analysis compared clinical outcomes between elective high-frequency oscillatory ventilation (HFOV) versus conventional ventilation (CV)

Recent a meta-analysis in 2015, 19 eligible studies involving 4096 preterm infants were included in **Figure 2**. Meta-analysis comparing elective HFOV with CV, bronchopulmonary dysplasia (BPD) and severe retinopathy of prematurity in survivors at term equivalent gestational age or discharge was significantly reduced with the use of HFOV. There was no evidence of effect on mortality at 28 to 30 days of age or at approximately term equivalent age. Pulmonary air leaks, defined as gross air leaks or pulmonary interstitial emphysema, occurred more frequently in the HFOV group but no difference in only gross air leaks. However, pulmonary air leaks were not different between HFOV and CV when subgroup analyses by age at randomization, routine surfactant use or not, type of high frequency ventilator (oscillator versus flow interrupter), inspiratory to expiratory (I:E) ratio of high frequency ventilator (1:1 versus 1:2) and CV strategy (lung protective or not).⁽¹⁾

NCT05682937 28/Dec/2022

Previous physiologic studies in non-intubation, Sighs are spontaneous deep inspirations characterized in infants by a biphasic pattern with an inspiratory reinforcement occurring at the end of an inspiration ('breath on the top of a breath'). Sighs were more frequent in preterm than in term infants and more so during Rapid eye movement (REM) sleep than non-REM sleep.⁽⁵⁾ Sighs in the preterm infant without lung disease were similar frequency in normal full-term infants (1.5 sighs per 10 minutes).^(6, 7) Therefore, sigh frequency in preterm infants increased with the degree of prematurity at birth and severity of BPD.⁽⁶⁾ Sigh breaths were much more frequent in infants than in adults.⁽⁸⁾

[figure not shown]

Fig. 3 True oscillation generated by the HFO option is sinusoidal; expiration is supported by active expiration to prevent air trapping. The result is smooth, precise, and gentle oscillation (3A). HFO-Sigh helps avoid atelectasis and can be triggered at preset intervals or performed manually as required, following suctioning maneuvers for example (3B).

Previous physiologic studies in intubated adults, sigh may improve lung function through improved lung elastance (increased gas exchange and lung volume, and decreased the respiratory drive)⁽⁹⁾ and enhance regional lung protection (decreased regional lung strain and intra-tidal ventilation heterogeneity).⁽¹⁰⁾ In an animal study, large inflations or sighs increased release of active surfactant.⁽¹¹⁾

In intubated animal study, rat took a spontaneously deep (sigh) breath which resulted in a rapid fall of pCO₂ (from 30 to 26 mm Hg).⁽¹²⁾ In intubated pediatric patients after major surgery, arterial pCO₂

decreased from pressure support ventilation (PSV, 39.3 ± 3.3 mm Hg) to "PSV + sigh" group (34.3 ± 4.6 mm Hg; p <0.001)⁽¹³⁾ while arterial pCO₂ was not significantly different in neonatal patients (PSV vs. PSV + sigh, mean \pm SD 42.3 \pm 3.7 vs 40.4 \pm 5)⁽¹⁴⁾ and adult patients (PSV vs. PSV + sigh, median [interquartile ranges] 44 [38, 49] vs. 43 [39, 47] mm Hg, p = 0.70).⁽¹⁵⁾

Besides pCO_2 level, sigh breaths improved oxygenation and lung mechanics in neonate. In crossover randomized controlled trial (RCT) from 11 neonates (median age 11.5 [8.7–74] days) after cardiac surgery, PSV + sigh mode significantly increased PaO_2/FiO_2 , inspiratory time and tidal volumes, and decreased oxygenation index and respiratory rate compared to PS mode.⁽¹⁴⁾ In 48 healthy preterm infants (weight at study 2,042 ± 316 g and postconceptional age 36.6 ± 2.0 weeks), mean ± SD. functional residual capacity (FRC) after sigh breaths, after apneic pauses, and neither a sigh nor an apneic pause was found 26.0 ± 6.9, 20.0 ± 6.8, and 24.0 ± 7.7 mL/kg, respectively, FRC after sigh breaths and neither a sigh nor an apneic pause was significantly higher than after apneic pauses.⁽¹⁶⁾

Knowledge gap

Due to the lack of data and complexity of ventilator management trials, a clear consensus for the optimum mode of initial mechanical ventilation for neonate does not exist. The ventilation strategies used for this population vary significantly. However, HFOV is increase used as an initial ventilatory strategy especially in preterm infants including our center. Study in HFOV combined with intermittent sigh breaths in neonate is limited especially on arterial carbon dioxide level.

There were only two active but not recruiting studies which compared between HFOV with intermittent sigh breaths (HFOV-sigh) and HFOV in ClinicalTrial.gov

(https://clinicaltrials.gov/ct2/results?cond=High+frequency+oscillatory+ventilation+with+intermittent+sigh+breath s+&term=&cntry=&state=&city=&dist=, Figure 4)^(17, 18) Both registered trials focus on preterm neonates (gestational age 24–36 weeks), sigh PIP 30 cm H₂O for 1 hour, and measured lung mechanics (electric tomography impedance) and blood oxygenation.^(17, 18) While this study fulfils this intervention by enrolled preterm and term infants (gestational age 24–41 weeks), lower sigh PIP (MAP+5, maximum sigh PIP 30 cm H₂O; usually MAP in HFOV 8–25 cm H₂O) for 2 hours, and focus on blood ventilation.

| | | | S. National Library of Medicine calTrials.gov | Find Studies ▼ A | About Studies 🕶 | Submit Studies - | Resources - Abc | out Site ▼ | PRS Login |
|-------|----------|-------------------------------------|---|------------------|--------------------------------------|-------------------------|--|----------------|-------------------|
| | | Home > | Saved Studies | | | | | Save | ed Studies (2) |
| | | | | Saved | Studies | | | | |
| Clear | Saved St | udies List | | | | | | | Download |
| | | | | | | | | | Show/Hide Columns |
| | | | | | | | | | |
| Row | Saved | Status | Study Title | | | Conditions | Intervention | ns | Locations |
| Row 1 | Saved | Status Active, not recruiting | Study Title High Frequency Oscillatory Ventilation Combined With I Lung Volume Monitored by Electric Tomography Imped | | Premature Bronchop Ventilator- | ry Distress Syndrome In | Intervention Other: HFOV comb sigh breaths | bined with • I | |

Fig. 4 Studies registered in ClinicalTrial.gov which compared "High frequency oscillatory ventilation with intermittent sigh breaths (HFOV-sigh)" with "High frequency oscillatory ventilation (HFOV)"

Objectives

Comparing the pCO_2 level after 2 hours of HFOV-sigh mode (after intervention) compared with HFOV mode (before intervention)

Conceptual framework

[figure not shown]

Fig. 5 Factors affect arterial pCO₂ level in ventilated neonates

(HFOV = High frequency oscillatory ventilation; PIP = Peak inspiratory pressure; RR = Respiratory Rate; Ti = inspiratory time)

Literature review

High-frequency oscillatory ventilation (HFOV) is a type of ventilator that can reduce barotrauma, achieve adequate alveolar ventilation with small tidal volumes. In recent years, HFOV versus conventional ventilation for acute pulmonary dysfunction in preterm infants had has been highly debated issue about effectiveness in many systemic reviews, meta-analyses, and randomized controlled trials.^(1, 19, 20) From meta-analysis, It revealed HFOV could reduce chronic lung disease or death rather than conventional ventilation.⁽¹⁾

Sighs are spontaneous deep inspirations characterized in infants by a biphasic pattern with an inspiratory reinforcement occurring at the end of an inspiration ('breath on the top of a breath'). Sighs were more frequent in preterm than in term infants and more so during Rapid eye movement (REM) sleep than non-REM sleep.⁽⁵⁾ Sighs in the preterm infant without lung disease were similar frequency in normal full-term infants (1.5 sighs per 10 minutes).^(6, 7) Therefore, sigh frequency in preterm infants increased with the degree of prematurity at birth and severity of bronchopulmonary dysplasia.⁽⁶⁾ Sigh breaths were much more frequent in infants than in adults^{.(8)}

Previous physiologic studies in intubated adults, sigh may improve lung function through improved lung elastance (increased gas exchange and lung volume, and decreased the respiratory drive)⁽⁹⁾ and enhance regional lung protection (decreased regional lung strain and intratidal ventilation heterogeneity).⁽¹⁰⁾ In an animal study, large inflations or sighs increased release of active surfactant.⁽¹¹⁾

Sigh breaths may improve CO_2 clearance,⁽¹³⁾ oxygenation and lung mechanics^(14, 16) in neonate. Currently, only 4 studies in HFOV-sigh mode were conducted. The first and second studies were registered in Clinical trial.gov.^(17, 18) Preterm (gestational age 24–36 weeks) neonates were enrolled to crossover RCT between HFV and HFV-sigh groups to compare oxygenation and lung volume in both periods. The sigh peak inspiratory pressure (PIP) was set at 30 cm H₂O. Both trials have still been active studies and outcome data not reported in the clinicaltrial.gov. The third study in Japan was a practical advice in preterm (especially for infants born at less than 28-week gestation). They applied sigh breaths (2-3 times per minute, 0.7-1.0 seconds in duration) with sigh PIP at 5 cm H₂O above the current mean airway pressure (MAP).⁽²¹⁾ The final study compared HFJV with or without sigh breath in neonate with respiratory distress syndrome (RDS) and meconium aspiration syndrome (MAS).⁽²²⁾

We hypothesized that sigh breaths augment restoring lung volume and ventilation in intubated neonate with HFOV. In neonatal studies, the results from HFOV combined with intermittent sigh breaths have never reported (active 2 studies and review 1 study).^(17, 18, 21) This study, therefore, was designed to examine the short-term effects of sigh breaths during HFOV in neonate undergoing mechanical ventilation.

Methods

Study design: before-after interventional, non-randomized trial, study

Study setting: Neonatal Intensive Care Unit (NICU), Songklanagarind Hospital

Target population: NICU admitted neonate

Study population: Intubated neonate

Inclusion criteria:

- Preterm and term neonate (gestational age 24-41 weeks) with postnatal age less than 28 days
- Already ventilated with high frequency ventilation at least 1 hours
- An umbilical or peripheral arterial catheterization was available

Exclusion criteria

- Previous or current pulmonary air leaks (pulmonary interstitial emphysema, pneumothorax, pneumomediastinum, and pneumopericardium)
- Heterogeneous lung disease including MAS, congenital diaphragmatic hernia
- Suspected lung hypoplasia
- Suspected or confirmed intraventricular hemorrhage grade III-IV
- Suspected or confirmed hypoxic ischemic encephalopathy or 5-min Apgar score less than 3
- Hemodynamic instability despite using inotrope(s)
- Arterial pCO₂ level less than 45 mm Hg or more than 70 mm Hg before intervention
- Need a new arterial puncture for samples both before and after interventions
- Moribund status
- Parents' decision not to participate

Subject withdrawal criteria

- Develop air leak syndrome during intervention
- Worsening respiratory distress with increasing HFO setting (changed Hz, MAP, delta pressure, increased FiO₂ more than 0.1, and need to suction or positive pressure ventilation via self-inflating bag or T-piece resuscitation) during study
- Hemodynamic instability and need to increase dose or add new inotrope during intervention
- Parents' decision not to participate during study

[figure not shown]
Study termination criteria

- During or after intervention within 24 hours, more than 5 neonates will develop new pulmonary air leaks (10% of 50 participants; because pulmonary air leaks occurred in HFOV 27.7% [392/1,415] in meta-analysis⁽¹⁾ so we use 10% of sample size calculation to terminate study for safety).
- The second sample after add sigh breath, more than 10 neonates have pCO₂ <35 mm Hg neonates (20% of 50 participants).

Sample size calculation

Primary outcome: Compare arterial pCO₂ level between HFOV (before) and HFOV-sigh (after)

- No previous study was compared the pCO₂ level between neonates who were on HFOV mode and HFOV + sigh mode.
- From Bonacina 2019,⁽¹⁴⁾ neonates who were on invasive PSV and PSV + sigh mode. The pCO₂ levels in PSV and PSV + sigh were 42.3 ± 3.7 mm Hg and 40.4 ± 5.0 mm Hg (Delta = 1.9 mm Hg, SD. = 4.35), respectively.

Study design was before and after intervention. The dependent outcome was pCO₂ level (continuous variable) In two dependent mean data, the calculated sample size was 42 neonates (alpha = 0.05, beta = 0.2, Delta = 1.9, SD. = 4.35), then increase 20% (if possible) for increased power. Finally, the targeted sample size was 50 neonates. We plan to recruit for one year, then preliminary analysis will do. If the result was significant differences, the study may be considered to terminate.

Operational definition

- Dependent variable = Arterial pCO₂ level
- Independent variables = Sigh breaths

Procedure

- Neonates who were ventilated with HFOV would be informed consent to the parents by the neonatal fellow ([name]). After informed consent, the first arterial blood gas was drawn after on HFOV at least 1 hour. Then, participants would be switched on HFOV-sigh mode (the same setting of HFOV mode and add only sigh breath). The second arterial blood gas was drawn (2 hours to 2 hours 15 minutes after start HFOV-sigh). After that sigh breaths would be switched off then on only HFOV mode.
- The ventilator in NICU had 4 brands (SLE6000, Drager, Fabian, and Sensor medic); however, sigh mode was only available in SLE6000 infant ventilators (United Kingdom) and Drager Babylog VN500 (Germany).
- HFOV-sigh setting both SLE6000 and Drager Babylog VN500: setting (Hz, MAP, delta pressure) same as HFOV, set sigh RR 3 breath/min, Sigh Ti = 1 sec, Sigh PIP = (MAP+5, maximum 30) cm

 H_2O , Slope sigh 0.5. No change in Hz, MAP, delta pressure, and increased FiO_2 less than 0.1 occurred between intervention.

Currently, only 3 studies in HFOV-sigh mode were conducted (Table 1). We set sigh RR 3 breath/min and Sigh Ti = 1 sec (similar to previous studies^(17, 18, 21)), Sigh PIP = (MAP+5,⁽²¹⁾ maximum 30^(17, 18)) cm H₂O. While HFJV combined with higher sigh PIP (set at 27 and 37 cm H₂O in RDS and MAS) resulted in excessive tidal volume.⁽²²⁾

| Author | Population | Mode of | Si | Sigh | | |
|-----------------------------|---------------------|------------|-----------------------|---------|---------|----------|
| | | ventilator | Sigh PIP | Sigh RR | Sigh Ti | Duration |
| | | | (cm H ₂ O) | (/min) | (sec.) | |
| Heiring ^(17, 18) | Preterm neonate | HFOV | 30 | 3 | 1 | 1 h |
| Nakanishi ⁽²¹⁾ | Preterm neonate | HFOV+VG | MAP+5 | 2-3 | 0.7-1.0 | N/A |
| Romo ⁽²²⁾ | Preterm and Term | HFJV | 27 (RDS) | 6 | 0.3-0.4 | N/A |
| | neonates | | 37 (MAS) | | | |
| Bonacina ⁽¹⁴⁾ | Neonate and infant | PSV | 30 | 1 | 3 | 240 |
| | | | | | | breaths |
| Nacoti (13) | Children undergoing | PSV | 30 | 1 | 0.5 | 1 h |
| | major surgery | | | | | |
| Mauri ⁽¹⁰⁾ | Adult with ARDS | PSV | 35 | 2,1,0.5 | N/A | 20 min |
| Mauri ⁽¹⁵⁾ | Adult with ARDS | PSV | 30 | 1 | N/A | 30 min |
| Badet ⁽²³⁾ | Adult with ARDS | A/C | <40, 2*TV | 2-3 | N/A | 1 h |

Table 1. Review sigh breaths in neonates, children, and adults with HFOV

A/C= assist controlled, HFJV = high-frequency jet ventilation; HFOV = High frequency oscillatory ventilation; VG = Volume guarantee; MAP = Mean airway pressure, MAS = Meconium aspiration syndrome; N/A = not available; PIP = peak inspiratory pressure; PSV = pressure support ventilation; RDS = Respiratory distress syndrome; RR = Respiratory rate; Ti = Inspiratory time; TV = tidal volume

• The monitoring during HFOV and HFOV-sigh monitoring was vital signs (systolic, diastolic, mean arterial pressure, heart rate, SpO₂ were collected every 15 minutes during intervention for 2 h and after intervention for 1 h) by neonatal fellow ([name]) and nurse, clinical manifestations, respiratory distress, umbilical arterial blood gas during study, and chest X-ray within 24 hours after intervention or immediately if clinical conditions deteriorate. The first blood gas was obtained after HFOV mode at least 1 hour with stable participants. After HFOV-sigh, the blood gas was obtained after 2 hours (no more than 2 hours 15 minutes) in this setting.

Data collection

Participant's data and blood gas's result will be recorded in record form.

Data management

EpiData entry is used for data entry and data documentation. The data will be safe and private collected; moreover, only principal investigator and recorder will access.

Data analysis

Parametric continuous variables are presented as mean (standard deviation, SD) and paired t-test was used to compare paired samples. Nonparametric continuous variables are presented as median (interquartile range, IQR) and the Wilcoxon signed rank test with continuity correction was used to compare paired samples. Subgroup analysis for gestational age less than 37 and 32 weeks.

Ethical issues

For Safety, the intermittent sigh breaths generated low sigh RR, optimal sigh PIP and Ti from previous studies. For 2 hours, neonatal fellow will monitor clinical conditions and then 24 hours after intervention. Risk of sigh breath may be air leak syndrome because this mode may increase PIP sigh and ventilation. In metaanalysis in neonate, neonates who on HFOV mode developed pulmonary air leaks 27.7% (392/1,415).⁽¹⁾ However, neonate with risk of air leak syndrome (previous or current pulmonary air leaks e.g., pulmonary interstitial emphysema, pneumothorax, pneumomediastinum, and pneumopericardium. Heterogeneous lung disease including MAS, congenital diaphragmatic hernia, and suspected lung hypoplasia) will be excluded and the participants will be closed-monitored during and 24 hours after intervention (clinical and radiographic conditions). Some neonates may expose X-ray (increase 1 time) more than routine care to monitor safety. However, some neonate may need follow X-ray by clinical condition of each neonate within 24 hours, this neonate will not be repeat more X-ray.

The blood gases were drawn for 2 times, more than routine care. The arterial blood gases were only drawn through umbilical or peripheral arterial catheter for reducing pain from direct artery puncture. Each time used approximately 0.2 mL of blood (Total blood 0.4 mL). Arterial blood gases were needed to evaluate patient's ventilation. In case of lowest birth weight 500 g neonate, total blood loss was about 0.8 mL/kg/day (< 2.5 mL/kg). The methods of arterial blood gas drawing were firstly the doctor would draw blood containing heparin from umbilical artery catheter to the first syringe by sterile technique then the tuberculin syringe was secondly drawing from umbilical artery catheter to be analyzed for arterial blood gas. Thirdly, the blood from the first syringe was returned to the patient and finally the blood was clear from umbilical or peripheral arterial catheter by 0.5 mL flushing with normal saline. The maximum allowable blood draw volumes were shown in **Figure 6**.

| Maximum allowable blood draw volumes: | | | | | | |
|---------------------------------------|-----|--------------|---------------------------------|----------------------------------|--|--|
| PATIENT'S WEIGHT | | TOTAL VOLUME | MAXIMUM mL IN ONE BLOOD DRAW | MAXIMUM mL IN A 30-DAY PERIOD | | |
| Kg | lbs | mL | 2.5% of total blood vol | 5% of total blood vol | | |
| 1 | 2.2 | 100 | 2.5 | 5 | | |

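### The air-leak stop is one fixed total for the whole study, so an early cluster of up to five leaks triggers no study-level action; a short count table by number treated would fix this cheaply

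*Combined protocol and SAP*

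**What the plan says.** Under Study termination criteria, the study ends if "more than 5 neonates will develop new pulmonary air leaks (10% of 50 participants", counting leaks during the intervention or in the 24 hours after it. The section cites a pooled HFOV leak rate of 27.7% (392/1,415) and adds: "so we use 10% of sample size calculation to terminate study for safety". A second, separate criterion counts infants with a low pCO2 on the second sample (more than 10, set as 20% of 50).

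The only other study-level look is under Sample size calculation: "We plan to recruit for one year, then preliminary analysis will do". It is tied to a significant result and carries no safety limit.

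Safeguards for the single infant are described elsewhere. Exclusion criteria remove infants with previous or current air leak, heterogeneous lung disease or suspected lung hypoplasia. Subject withdrawal criteria remove an infant who develops an air leak during the intervention. Procedure requires a chest X-ray within 24 hours, and Ethical issues describes clinical and radiographic monitoring over the same period. No section gives a leak limit by number treated or an enrolment pause, or says who reviews the running count and when.

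**The concern.** The plan justifies its air-leak limit as a rate (10%) but applies it as a total. The two agree only near full enrolment. Early in the trial, a leak frequency far above 10% can build up while the count stays at 5 or below.

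This matters because Ethical issues names air leak as the risk of sigh breaths, the literature review says that neonatal results for HFOV with sighs have not been reported, entry goes down to 24 weeks, and there is no concurrent control group. Withdrawal and monitoring protect the infant who has the leak. They do not make the study stop and look before the next infant is enrolled.

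**Working it through.** **1. The plan's own figures.** 0.10 × 50 = 5 and 392/1,415 = 0.277, as stated. More than 5 means that the sixth leak triggers.

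**2. What the cap lets through.** 5 of 10 is 50% and 5 of 20 is 25%; neither triggers. If the true rate were exactly 10%:
- P(5 or more of 10) = Σ C(10,k) 0.1^k 0.9^(10−k) for k ≥ 5 = 0.0016
- P(5 or more of 20) = Σ C(20,k) 0.1^k 0.9^(20−k) for k ≥ 5 = 0.043

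Both would be unusual at the rate the plan treats as its limit.

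**3. Rules compared, with 50 infants.**
- Current: act at the sixth leak, at any time.
- Illustration: the same ceiling, plus a check at infants 10, 15, 20, 25 and 30 that pauses enrolment at 3, 4, 4, 5 and 5 leaks or more.

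**4. Method.** For true rate p, let f_n(k) be the probability of k leaks after n infants with no action so far, and f_0(0) = 1. Each new infant gives g_n(k) = (1−p) f_{n−1}(k) + p f_{n−1}(k−1). The probability of first action at infant n is s_n = Σ g_n(k) over k ≥ c_n, and f_n keeps the rest. Here c_n = 6 throughout for the current rule. For the illustration c_n is 3, 4, 4, 5, 5 at infants 10, 15, 20, 25, 30 and 6 otherwise. Mean treated before first action = Σ n s_n + 50(1 − Σ s_n), and mean leaks = p × mean treated. For the current cap this agrees with the binomial tail: at p = 0.20, P(6 or more of 20) = 0.196 and P(6 or more of 50) = 0.952.

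Assumptions: infants are independent, and each outcome is known before the next infant is treated. The documents give no 24-hour leak rate, so every value of p is an assumption. The cited 27.7% has no stated period and is not used.

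**5. Results (current → with table).**

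| True rate | Action by infant 20 | Action ever | Mean treated before first action |
|---|---|---|---|
| 3% | <0.001 → 0.005 | 0.004 → 0.008 | 50.0 → 49.8 |
| 5% | <0.001 → 0.022 | 0.038 → 0.053 | 49.7 → 48.9 |
| 10% | 0.01 → 0.15 | 0.384 → 0.416 | 45.5 → 41.9 |
| 20% | 0.20 → 0.61 | 0.952 → 0.957 | 29.6 → 22.6 |

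At 20%, mean leaks before first action are 0.2 × 29.6 = 5.9 and 0.2 × 22.6 = 4.5.

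**The case against.** **The comparison favours the table.** The current rule ends the study; the table only pauses it. If the pause is lifted, enrolment can run on to the same sixth leak and the saving can fall to nothing. This stands. The 7.0 infants (29.6 − 22.6) and 1.4 leaks (5.9 − 4.5) are the most that could be saved, and the chance of ever acting hardly moves.

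**A 20% rate is not supported by the documents.** Exposure lasts about 2 hours, and infants at known risk of leak are excluded. This also stands. At a true 3% the table changes almost nothing (0.8% against 0.4% ever). Its value is insurance against a rate that nobody yet knows.

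**A running count is feasible already.** This is a single unit, a neonatal fellow follows each infant, and the cap can fire on any infant. That is true, but a sixth leak is still needed, and no one is assigned to keep or review the tally.

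**Stronger readings that a reader might infer.**
- That the cap is checked only at the end. It is worded as a count, so 6 leaks in the first 6 infants would stop the study.
- That both termination limits are slow to react to air leaks. Only the first counts leaks.
- That low pCO2 needs the same running check. The exclusions cover a "level less than 45 mm Hg or more than 70 mm Hg before intervention", so a value below 35 needs a fall of more than 10 mm Hg. With the planning inputs ("beta = 0.2, Delta = 1.9, SD. = 4.35", treated as normal), the chance at a baseline of 45 is Φ((35 − 43.1)/4.35) = 0.031. With the 5.0 mm Hg fall cited for children (39.3 − 34.3) it is Φ(−5/4.35) = 0.125, or 6.25 expected in 50 even if every infant started at 45. The case for a running check is weak.
- That the limit must be recalculated for 42 infants because the increase to 50 is qualified ("then increase 20% (if possible) for increased power"). The stated target is 50. A smaller final size would not be known while infants are being treated, and a lower count would conflict with keeping the existing ceiling.

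**Conclusion.** The point holds for air leaks only, and as a design improvement. The stated figures are correct. The gap is that up to five leaks, however early and however concentrated, lead to no action at study level.

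A short count table makes early action about three times as likely if the leak rate is high (0.61 against 0.20 by infant 20 at an assumed 20%), with little extra interruption if it is low (5.3% against 3.8% ever at 5%). The main cost falls at a true 10%, where the table pauses enrolment by infant 20 with probability 0.15 against 0.01. The conclusion that an early cluster goes unanswered rests on the wording alone; the size of the benefit rests on assumed rates and on what the review decides after a pause.

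**What to change.** Keep the existing ceiling of more than 5 leaks. Add to Study termination criteria a pre-stated tally check every 5 infants from infant 10. It would pause enrolment for review, not terminate the study, when leaks are high for the number treated. One illustration is 3 by infant 10, 4 by infant 15 or 20, and 5 by infant 25 or 30; the sponsor and its safety reviewers may set other counts. Name the person or group who reviews the tally, say when they do so, and state what is needed to lift a pause and that the ceiling still applies afterwards.

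The input is already collected (the chest X-ray within 24 hours), so the work is one small table and a running count. The price is some unneeded pauses, as shown in the working; a pause can be lifted, so each costs less than a termination. No change is needed to the low-pCO2 limit, to the target of 50, or to the care of any infant.

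### The paired sample size uses the average of two condition SDs (4.35) in place of the SD of within-infant differences, so the stated 80% power at 42 infants is unsupported

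*Combined protocol and SAP*

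**What the plan says.** The Sample size calculation section takes its inputs from a study of pressure support ventilation (PSV) with and without sighs, which it reports as "42.3 ± 3.7 mm Hg and 40.4 ± 5.0 mm Hg (Delta = 1.9 mm Hg, SD. = 4.35". It describes the comparison as one of two dependent means and concludes that "the calculated sample size was 42 neonates (alpha = 0.05, beta = 0.2, Delta = 1.9, SD. = 4.35". The number is "then increase 20% (if possible) for increased power", which gives the target of 50.

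Under Data analysis, for continuous variables treated as parametric, the "paired t-test was used to compare paired samples". The Background and rationale describes the source study as a "crossover randomized controlled trial (RCT) from 11 neonates", so each source infant was measured under both conditions. Neither an SD of within-infant differences nor a within-infant correlation is given anywhere in the document.

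**The concern.** The power of a paired t-test depends on how much the change in pCO₂ varies from infant to infant. It does not depend directly on how much pCO₂ varies between infants under each condition. The figure of 4.35 sits beside the two condition SDs and looks like their average. If it is, the calculation put a between-infant spread where the paired formula needs the spread of the differences.

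This is the only power justification for the primary outcome. If the input is wrong, the stated beta of 0.2 at 42 infants rests on an assumption that the plan neither states nor defends. A reader of a non-significant result could then take it as coming from a trial with 80% power to detect 1.9 mm Hg when that was never established.

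**Working it through.** **Inputs from the Sample size calculation section.** Alpha 0.05, beta 0.2, mean difference 42.3 − 40.4 = 1.9 mm Hg, condition SDs 3.7 and 5.0, SD used 4.35. The section does not say whether the test is two-sided. Two-sided is inferred because it reproduces the plan's 42, whereas one-sided gives 33.

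**Step 1: where 4.35 comes from.** (3.7 + 5.0)/2 = 4.35 exactly. A root-mean-square pooled SD would be √((3.7² + 5.0²)/2) = 4.40.

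**Step 2: reproduce the plan's figure.** The paired normal-approximation formula is n = ((z₀.₉₇₅ + z₀.₈₀) × SD / Δ)². With the plan's values:

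((1.960 + 0.842) × 4.35 / 1.9)² = 41.14, rounded up to 42.

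This matches. An independent-groups formula with the same inputs would give 83 per arm, so 4.35 was used as the SD of differences. The 20% increase gives 42 × 1.2 = 50.4, stated as 50.

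**Step 3: the quantity the formula needs.** For condition SDs s₁ and s₂ with within-infant correlation r,

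SD_diff = √(s₁² + s₂² − 2·r·s₁·s₂) = √(13.69 + 25 − 37r).

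Setting this equal to 4.35 gives r = (13.69 + 25 − 18.92)/37 = 0.534. At a lower r, 42 is too few; at a higher r, it is more than needed.

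**Step 4: the range.** Because the documents give no r, the values below are assumptions. Power and required n come from the noncentral t distribution (two-sided alpha 0.05, Δ = 1.9).

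| Assumed r | SD of differences (mm Hg) | Power, n = 42 | Power, n = 50 | n for 80% power |
|---|---|---|---|---|
| 0 (extreme bound) | 6.22 | 0.49 | 0.56 | 87 |
| 0.3 | 5.25 | 0.63 | 0.71 | 62 |
| 0.5 | 4.49 | 0.76 | 0.83 | 46 |
| 0.534 (plan's implicit value) | 4.35 | 0.79 | 0.86 | 44 |
| 0.7 | 3.58 | 0.92 | 0.96 | 30 |

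**Step 5: thresholds.** For 80% power, the SD of differences can be at most 4.29 with 42 infants (r of about 0.55) and at most 4.70 with 50 (r of about 0.45).

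The row at r = 0.534 also shows a minor gap from the normal approximation. Even if 4.35 is right, power at 42 is 0.79, and 80% needs 44.

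**The case against.** The strongest reply has four parts.

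- **The implied correlation is plausible.** A value near 0.53 is not unreasonable for two blood gases from the same infant about two hours apart with settings held. This stands, and it is why the finding is an undocumented assumption and not a demonstrated shortfall. The row at r = 0 is only a bound and carries little weight.
- **The operative number is 50, not 42.** At 50, power is 0.86 with an SD of 4.35 and 0.83 at r = 0.5. This stands in part. The increase is qualified in the plan ("then increase 20% (if possible) for increased power") and is not offered as a correction for this input. At r = 0.3, 50 infants still give only 0.71.
- **A null result will be read from its confidence interval.** The trial's own paired data will supply the SD of differences, and planned power does not govern that reading. This is fair and limits the harm. It does not supply the missing basis for the power claim.
- **Varying r alone understates the uncertainty.** This also stands. The SDs come from a different ventilation mode, in a small study whose mean of 42.3 mm Hg under PSV lies below this trial's entry floor (exclusion for a "level less than 45 mm Hg or more than 70 mm Hg before intervention"). For illustration only, assumed SDs of 6 in both conditions give SD_diff = 6√(2(1 − r)). Power at 50 is then about 0.46, 0.59 and 0.81 for r = 0.3, 0.5 and 0.7. Whether the source SDs carry over is a separate question, but it is a further reason to state the SD of differences openly.

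**Conclusion.** The concern holds. The calculation is carried out correctly on the wrong input: 4.35 is the average of two condition SDs, and the paired test needs the SD of within-infant differences. The two coincide only at a correlation of about 0.53, which the plan does not state.

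With the source SDs, and r assumed between 0.3 and 0.7, power for 1.9 mm Hg runs from 0.63 to 0.92 at 42 infants and from 0.71 to 0.96 at 50. The direction of the error is unknown. The target of 50 absorbs a moderate error, down to r of about 0.45, provided that 50 complete pairs are reached and the source SDs apply. This should be corrected, but it does not by itself invalidate the design.

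**What to change.** In the Sample size calculation section, replace the SD of 4.35 with an explicit SD of within-infant differences. Take it from the source crossover study if that study reports one; otherwise give the two condition SDs with a stated assumed correlation. Say that the test is two-sided, and give power as a range. Suggested wording:

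> With condition SDs of 3.7 and 5.0 mm Hg and an assumed within-infant correlation of 0.3, 0.5 or 0.7, the SD of differences is 5.25, 4.49 or 3.58 mm Hg. Power to detect a 1.9 mm Hg difference (two-sided alpha 0.05, paired t-test) is 0.63, 0.76 or 0.92 with 42 infants and 0.71, 0.83 or 0.96 with 50. The difference detectable with 80% power with 50 infants is 2.1, 1.8 or 1.4 mm Hg. The source infants had a mean pCO₂ of 42.3 mm Hg under PSV, below this trial's entry floor of 45 mm Hg, so the spread may differ from that assumed here.

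A further line with larger condition SDs would show how far the range depends on the source study. Keep the target of 50.

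The cost is one reworded paragraph; the target, test and procedures do not change. The stated power becomes a range and may look less favourable than a single 80%.
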